6.2 Randomization, blinding and treatment allocation

All consecutive patients meeting the inclusion criteria will be asked to participate in the study. After the first outpatient clinic visit informed consent will be obtained by the hand surgeon or the investigator of the study site. Computerized randomization will be performed as soon as written informed consent is provided, with Castor EDC. In trials comparing surgery with non-operative management, blinding of patients and surgeons is not possible and therefore randomization of this study is not blinded.

6.3 Study procedures

A detailed description of the procedures is provided under 6.1 Study parameters. A summary of the procedures, including time intervals and standard procedures / procedures for study purposes interval, is provided in Figure 2. below.

V7 01-02-2024 20 of 30

Description of visit	Measurements	
	Hand function	Questionnaires
First OPD visit Handsurgeon confirms diagnosis complete UCL rupture Inclusion & randomization		MHQ PSFS EQ-5D short iPCQ
OPD visit, removable cast, refferal to handtherapy	ROM	MHQ PSFS
*	-	EQ-5D iPCQ, iMCQ
OPD visit, evaluation of treatment outcome	ROM Grip and pinch strength	MHQ PSFS EQ-5D iPCQ, iMCQ
	First OPD visit Handsurgeon confirms diagnosis complete UCL rupture Inclusion & randomization OPD visit, removable cast, refferal to handtherapy - OPD visit, evaluation of	First OPD visit Hand function First OPD visit Handsurgeon confirms diagnosis complete UCL rupture Inclusion & randomization OPD visit, removable cast, refferal to handtherapy OPD visit, evaluation of treatment outcome Hand function ROM ROM Grip and

Figure 2.

6.4 Withdrawal of individual subjects

Subjects can leave the study at any time for any reason if they wish to do so without any consequences. The investigator can decide to withdraw a subject from the study for urgent medical reasons. All withdrawals and dropouts of enrolled subjects from the trial are reported and explained on the CRFs.

6.5 Replacement of individual subjects after withdrawal

Study inclusion continues until 114 participants completed the intervention as well as all assessments.

6.6 Follow-up of subjects withdrawn from treatment

When subjects withdraw from treatment, data of the subject will be used up until the time of withdrawal for analysis, according to the intention-to-treat principle to obtain a complete database of consecutive patients and to avoid attrition bias.

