4.4 Sample size calculation

This sample size calculation is based on our primary endpoint (hand function at 6 months expressed as MHQ score 6 months after injury) and calculated using G Power 3.1.9.2. The MHQ score of an individual without any complaints of the hand is 100. The lowest score, indicating worst pain and severe impairment, is zero. The hypothesis will be assessed using a non-inferiority design. The results from two earlier studies on the subject were used for sample size calculation. [4,5] We used a one-sided significance level of 0.025 and a power of 80% with a standard deviation (SD) of 15, and setting our non-

V7 01-02-2024 12 of 30

inferiority limit at 8. The non-inferiority limit of 8 is based on the previous estimated minimal clinically important difference (MCID) of 15 points, divided by 2 and rounded up to 8. A total of 114 patients will be needed to demonstrate non-inferiority of our hypothesis. Each treatment arm will need 57 patients. Including consideration for a potential 10% loss to follow-up, the total number of patients to be included, set at 114, is multiplied by a factor of 1.10. This results in a total of 126 patients to be included.". The MCID of 15 is based on the average of the MCID's of 23, 13 and 8 for the pain, function and work domains, respectively in patients with carpal tunnel syndrome (CTS). [4] The MCID in MHQ score for patients with thumb injury is not yet investigated. Therefore, we decided to use the MCID of CTS patients.

Considering the uncertain outcome of the control group treatment in terms of MHQ-scores for patients with UCL-ruptures, an independent statistician will assess if the sample size calculation needs adjustment, based on the mean change in MHQ-score and SD in the control group, after half of the patients past their 6-month follow-up (N=28).

V7 01-02-2024 13 of 30

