7. STATISTICAL ANALYSIS

Data will be analyzed following intention-to-treat. Categorical variables will be presented as counts and percentages and continuous variables as median and interquartile ranges or mean and standard deviation based on the normality of the data. Differences in characteristics between groups will be compared using Fisher exact and Pearson's χ^2 tests for categorical variables, and Wilcoxon rank sum tests and unpaired t test will be used for continuous variables, where appropriate.

We will conduct a linear regression analysis for longitudinal data (i.e. a mixed model) in which we correct for relevant prognostic factors (age, sex, time between trauma and definite treatment, duration of hand therapy) and baseline scores of the Michigan Hand Questionnaire. In an additional step, we will correct for surgeons depending on the number of treating surgeons as well as the number of patients per treating surgeon. Results will be presented as differences between treatment and control with 95% Confidence intervals. The intervention will be labeled as non-inferior when the noninferiority margin of 8 lies outside the 95% CI of this difference, regarding the Michigan Hand Questionnaire measured at 6 months as our primary endpoint. In case missing data did not happen randomly, but was related to specific factors (e.g. more missing data for men than for women), we will correct for this. In an additional analysis, the absolute MHQ scores at 6 months will be adjusted for differences in baseline MHQ scores between the intervention and control group. The secondary outcomes: PSFS, EQ5D, ROM, Kapandji score, grip strength, pinch strength and pain will be analyzed in a similar manner. Differences between the two treatment groups in complication rates will be analyzed using the Chi-square test or the Fischer's Exact test (in case the expected incidence was less than five).

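### Section 6.6 cuts off data when a patient withdraws from treatment and calls this intention-to-treat; as written, it removes the 6-month primary outcome of patients who stop or refuse treatment

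*Protocol*

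**What the plan says.** Section 6.6 is headed as concerning subjects withdrawn from treatment. Its rule is: "When subjects withdraw from treatment, data of the subject will be used up until the time of withdrawal for analysis". The reason given is that this is done "according to the intention-to-treat principle to obtain a complete database of consecutive patients and to avoid attrition bias".

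Other parts of the protocol bear on it:

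- Section 7: "Data will be analyzed following intention-to-treat". The non-inferiority decision rests on that analysis: "The intervention will be labeled as non-inferior when the noninferiority margin of 8 lies outside the 95% CI of this difference". The endpoint is the MHQ at 6 months.
- Section 6.4 deals separately with subjects who leave, or are taken out of, the study.
- Section 6.5 keeps recruitment open until 114 participants have completed both the intervention and every assessment.
- Section 5.1 gives 4 weeks of fixed cast and 4 weeks of removable cast in both arms, after surgery in the control arm. Cast patients without a clear firm endpoint at the 2-week examination go on to surgery, which the section describes as a switch to usual care.
- Section 6.1.2 schedules the MHQ at randomisation, after 4 weeks of immobilisation, and at 3 and 12 months, in addition to 6 months. Questionnaires can be completed by post or online.

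**The concern.** Intention-to-treat means that every randomised patient is followed and analysed in the allocated arm, whatever treatment was received. A rule that stops using a patient's data once treatment is abandoned conflicts with that principle. It also creates missing outcomes, although its stated purpose is "to obtain a complete database of consecutive patients and to avoid attrition bias".

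The timing makes this more than a matter of wording. Allocated treatment is largely over by about 8 weeks, so withdrawal from it will normally precede the 6-month endpoint. The trial is open-label (section 6.2), so the decision to stop or refuse may depend on the known allocation and on how the thumb is doing. If patients who are cut off differ in prognosis between arms, the estimated difference is biased, and the 2.5% one-sided error behind the non-inferiority claim is no longer assured.

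Section 6.5 follows the same completer logic: a patient who is fully assessed but did not complete the allocated treatment does not count towards the target of 114.

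**Working it through.** **1. The plan's own figure.** Section 4.4 gives a margin of 8 and states: "We used a one-sided significance level of 0.025 and a power of 80% with a standard deviation (SD) of 15". With a true difference of 0, the normal approximation is

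n per arm = 2 × (1.960 + 0.842)² × 15² / 8² = 55.2, rounded up to 56.

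The noncentral t calculation gives power of 79.9% at 56 and 80.6% at 57. The stated 57 per arm (114 in total) therefore reproduces, and 114 × 1.10 = 125.4 gives the stated 126. The sample size is not in dispute.

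**2. What the rule removes.**

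- A patient who refuses surgery after randomisation has only the baseline MHQ, because the next is due after 4 weeks of immobilisation. Section 7 uses baseline MHQ as a covariate, so this patient brings no outcome to the model.
- A patient who abandons the cast during weeks 4 to 8 may have the 4-week score but loses the 3-, 6- and 12-month scores.
- In both cases the primary outcome is absent.

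**3. Size, on assumed rates.** The protocol gives no rate of stopping or refusing treatment. Let a share w of the cast arm be cut off, with a mean 6-month MHQ g points below the remaining cast patients. Then:

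- Full cast-arm mean = mean of those remaining − w × g, so the bias in favour of the cast is w × g.
- SE = 15 × √(1/57 + 1/(57 × (1 − w))).
- With the true deficit exactly at the margin of 8, P(declare non-inferior) = Φ(w × g / SE − 1.960).

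This assumes no loss in the surgery arm and no recovery from earlier visits. For w = 10%, SE = 15 × √(1/57 + 1/51.3) = 2.887:

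- g = 8: bias 0.8; Φ(0.277 − 1.960) = 0.046
- g = 15: bias 1.5; Φ(0.520 − 1.960) = 0.075

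| Share of cast arm cut off | g = 8 | g = 15 |
|---|---|---|
| 5% | 0.034 | 0.045 |
| 10% | 0.046 | 0.075 |
| 15% | 0.061 | 0.117 |

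The nominal value is 0.025. Simulation with t intervals gave 0.046 and 0.073 for the 10% row, and 0.115 for 15% with a 15-point gap.

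**4. The other directions.** If both arms lose the same share with the same gap, the biases cancel (w × g − w × g = 0). If instead 10% of the surgery arm is cut off with gaps of 8 to 15, the bias of 0.8 to 1.5 runs against the cast. When the treatments are truly equal, power becomes:

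- no bias: Φ(8/2.887 − 1.960) = 0.79
- bias 0.8: Φ(7.2/2.887 − 1.960) = 0.70
- bias 1.5: Φ(6.5/2.887 − 1.960) = 0.61

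**The case against.** **The rule may mean leaving the study.** Section 6.4 describes study withdrawal and sections 6.5 and 6.6 follow directly. Using data up to the point of leaving the study would be ordinary and unavoidable, and the aim of a complete database fits keeping what was collected. Section 6.6 also does not say that visits or questionnaires stop. This may be what the authors intended, but both the heading and the sentence say treatment, and leaving the study already has its own section. If study withdrawal was meant, the text still needs correcting, because sites will act on what is written.

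**The analysis may recover some information.** The mixed model uses earlier MHQ scores, and section 7 undertakes to correct for missingness related to specific factors. This stands for patients with a 4-week or 3-month score, so the figures above are upper values for their assumptions. It does not help a patient with a baseline score only. No method is named, and outcomes that are never collected cannot be restored.

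**Departures may be few.** Consent follows a period of reflection and precedes randomisation, and a cast patient who is not healing is offered surgery within the strategy. This is fair. No rate is documented beyond the 10% allowance for loss to follow-up, so frequent, outcome-related refusal cannot be asserted.

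**A reader might infer more:** that intention-to-treat is the only analysis, and that without a per-protocol analysis unoperated surgery-arm patients could dilute the difference into false non-inferiority. The documents do not support this.

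- Section 7 does not say that no other analysis set will be used. Supportive sets are commonly defined in the SAP, which is not available here, and requiring both analyses to agree is a debatable convention.
- Dilution arises only when non-adherent patients are kept in the analysis. Under section 6.6 as written they are cut off, so the two mechanisms cannot be added for the same patient.

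An error rate of about 10% can also be produced at 10% loss, but only by assuming a 20-point gap confined to the cast arm and no recovery from the model. That gap exceeds the protocol's own minimal clinically important difference of 15.

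**Conclusion.** Section 6.6 is wrong as written. It ends the use of data at withdrawal from treatment, attributes this to a principle that requires the reverse, and conflicts with section 7. This conclusion rests on the text and the visit schedule alone, not on any assumed rate or on the content of an SAP.

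The numerical effect is an illustration. With 10% of the cast arm cut off, a gap of 8 to 15 points, no comparable loss in the surgery arm and no recovery through the mixed model, the false non-inferiority rate is about 4.6% to 7.5% against a nominal 2.5%. The sign is not fixed: balanced loss does no harm on average, and loss of poor-outcome surgery patients would count against the cast. False non-inferiority is therefore one possible result, not a predicted one. The absence of a per-protocol analysis is not part of this conclusion.

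**What to change.** - **Rewrite section 6.6.** Patients who stop, refuse or change the allocated treatment stay in follow-up, have the MHQ collected at all visits including 6 months, and are analysed in the arm to which they were randomised. Data end only when a patient withdraws consent to follow-up.
- **Name the 2-week group.** State that cast patients operated on after the 2-week examination (about 1 in 10 expected, per the Summary) are within the tested strategy and are not withdrawn from treatment. The description in section 5.1 of a switch to usual care leaves this open.
- **Align section 6.5.** Count participants with the 6-month primary endpoint towards 114, rather than those who completed the intervention and every assessment.

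A per-protocol analysis may be given as supportive in the SAP, but this correction does not depend on it. The cost is amendment wording and some extra contact with patients who have left treatment; the postal and online questionnaires already exist. The change should be made early, because an outcome that was not collected cannot be restored at the analysis stage.

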6.7 Premature termination of the study

There will be no early assessment for efficacy or futility. We further assume that both treatment strategies are sufficiently safe. The risk of a surgical procedure in the intervention group is acceptable, considering that each patient in the control group will receive such operation upfront. Hence, we strive for a full completion of the study.

V7 01-02-2024 21 of 30

SAFETY REPORTING

6.8 Temporary halt for reasons of subject safety

In accordance to section 10, subsection 4, of the WMO, the sponsor will suspend the study if there is sufficient ground that continuation of the study will jeopardize subject health or safety. The sponsor will notify the accredited METC without undue delay of a temporary halt including the reason for such an action. The study will be suspended pending a further positive decision by the accredited METC. The investigator will take care that all subjects are kept informed.

6.9 AEs and SAEs

6.9.1 Adverse events (AEs)

Adverse events are defined as any undesirable experience occurring to a subject during the study, whether or not considered related to the trial procedure or the intervention, conservative treatment. All adverse events reported spontaneously by the subject or observed by the investigator or his staff will be recorded.

6.9.2 Serious adverse events (SAEs)

A serious adverse event is any untoward medical occurrence or effect that

- results in death;
- is life threatening (at the time of the event);
- requires hospitalization or prolongation of existing inpatients' hospitalization;
- results in persistent or significant disability or incapacity;
- any other important medical event that did not result in any of the outcomes listed above due to medical or surgical intervention but could have been based upon appropriate judgment by the investigator.

An elective hospital admission will not be considered as a serious adverse event. The investigator will report all SAEs to the sponsor without undue delay after obtaining knowledge of the events.

The sponsor will report the SAEs through the web portal *ToetsingOnline* to the accredited METC that approved the protocol, within 7 days of first knowledge for SAEs that result in death or are life threatening followed by a period of maximum of 8 days to complete the initial preliminary report. All other SAEs will be reported within a period of maximum 15 days after the sponsor has first knowledge of the serious adverse events.

V7 01-02-2024 22 of 30

6.10 Follow-up of adverse events

All AEs will be followed until they have abated, or until a stable situation has been reached. Depending on the event, follow up may require additional tests or medical procedures as indicated, and/or referral to the general physician or a medical specialist. SAEs need to be reported till end of study within the Netherlands, as defined in the protocol.

6.11 Data Safety Monitoring Board (DSMB)

Not applicable for this study.

V7 01-02-2024 23 of 30

7. STATISTICAL ANALYSIS

Data will be analyzed following intention-to-treat. Categorical variables will be presented as counts and percentages and continuous variables as median and interquartile ranges or mean and standard deviation based on the normality of the data. Differences in characteristics between groups will be compared using Fisher exact and Pearson's χ^2 tests for categorical variables, and Wilcoxon rank sum tests and unpaired t test will be used for continuous variables, where appropriate.

We will conduct a linear regression analysis for longitudinal data (i.e. a mixed model) in which we correct for relevant prognostic factors (age, sex, time between trauma and definite treatment, duration of hand therapy) and baseline scores of the Michigan Hand Questionnaire. In an additional step, we will correct for surgeons depending on the number of treating surgeons as well as the number of patients per treating surgeon. Results will be presented as differences between treatment and control with 95% Confidence intervals. The intervention will be labeled as non-inferior when the noninferiority margin of 8 lies outside the 95% CI of this difference, regarding the Michigan Hand Questionnaire measured at 6 months as our primary endpoint. In case missing data did not happen randomly, but was related to specific factors (e.g. more missing data for men than for women), we will correct for this. In an additional analysis, the absolute MHQ scores at 6 months will be adjusted for differences in baseline MHQ scores between the intervention and control group. The secondary outcomes: PSFS, EQ5D, ROM, Kapandji score, grip strength, pinch strength and pain will be analyzed in a similar manner. Differences between the two treatment groups in complication rates will be analyzed using the Chi-square test or the Fischer's Exact test (in case the expected incidence was less than five).

In theory, surgery in the intervention arm could result in an unexpectedly suboptimal outcome compared to immediate surgery. To determine whether this is the case, an exploratory analysis will be performed by ranking the changes in MHQ in the entire group of patients who (eventually) underwent surgery and comparing the mean rankings. If the mean ranking of the subgroup that eventually underwent surgery in the intervention arm indicates a suboptimal outcome (mean ranking more than 2 different in the direction of worsening to the detriment of the intervention arm), a critical event committee will be established to assess, based on a relevant extract from the patient file, whether direct surgery would have resulted in a different outcome. To increase the uncertainty for the committee and to avoid assessment bias, several directly operated patients from the control group will also be added to the set to be assessed. The qualitative reporting of the CEC assessment will be of a descriptive nature.

V7 01-02-2024 24 of 30

COST EFFECTIVENESS ANALYSIS

This evaluation focuses on the question if the proposed intervention for patients with a complete UCL rupture, including Stener Lesions, using initial nonoperative treatment, is cost-effective compared to operative treatment. The economic evaluation will be performed as a cost-effectiveness (CEA) as well as a cost-utility analysis (CUA) from the societal as well as health care perspectives. [13] The primary economic outcome for the CEA is the costs per unit change in overall hand function and closely relates to the clinical outcome measure. The CEA is performed to enable identification of diagnostic or interventional strategies to be preferred economically in the field of hand surgery. The primary economic outcome for the CUA is the costs per quality adjusted life year (QALY). The CUA is performed to enable priority setting during health care policy making across disease areas and health care settings.

If the null hypothesis in this study of nonoperative treatment not being clinically non-inferior at six months is not rejected, but indeed lower costs are associated with nonoperative treatment, then incremental cost-effectiveness ratios will be calculated as the extra savings per extra unit in MHQ score lost or the extra savings per additional QALY lost. If the null hypothesis is rejected, a costs analysis and an outcome analysis will be done as distinct partial economic evaluations. The time horizon will be 12 months. It is expected that effects and costs beyond 12 months are similar for both treatment strategies and that a lifetime time horizon is redundant.

Differences between groups will be assessed after correction for bias and using accelerate non-parametric bootstrapping to account for sampling variability, generating 5,000 replications. Results will be presented graphically by cost-effectiveness planes. Cost-effectiveness acceptability curves will be drawn for various levels of willingness-to-pay per QALY up to €50,000, because higher levels cannot be justified by the maximum observable disease burden in this target group of patients. A scenario analysis will be applied by excluding the productivity losses following sick leave. Subgroup analyses will be performed for patients with a paid job.

Missing cost and effect data will be imputed using multiple imputation according to the MICE algorithm developed by van Buuren. Rubin's rules will be used to pool the results from the different multiply imputed databases. [14]

Measurement and valuation of costs

We will gather data on the use of resources and the related costs regarding health care (e.g. medical specialist, hand-physiotherapist, treatment of complications), productivity losses (absenteeism (sick leave) and presenteeism (lowered efficiency while at work due to sick leave from work and lowered productivity while a work)) and out-of-pocket

V7 01-02-2024 25 of 30

expenses by patient and family members (e.g. health related travel, extra private help). The Dutch iMTA Medical Consumption Questionnaire and iMTA Productivity Cost Questionnaire will be adapted to and prepared for the current study setting and disseminated to patients for completion after two, three, six and twelve months of follow up.(11,12) Case report forms or electronic patient dossiers will be used to gather inhospital data. Unit costing will be based on the most recent Dutch guideline on costing in health care research at the time of data analysis. Costing of productivity losses will adhere to the friction costs approach with the current friction period at time of analysis.(13) The base year for costing will be 2022, with unit costs price-indexed if originating from other calendar years.

Patient outcome analysis

Patient outcome analysis in addition to the clinical outcome measures relevant to patients (disability, pain, hand function) the economic evaluation will include the measurement of health status at baseline (within 2 weeks after trauma), at two, three, six and 12 months after injury with the EQ-5D-5L. [15] This questionnaire consists of 5 items, measuring (at 5-point scales) whether patients experience problems, and if so, to what extent with regard to mobility, self-care, daily activities, pain/complaints, and mood. Existing health valuation scoring algorithms (Dutch reference values available through www.euroqol.org) will be used to assign a health utility to each 5-items score pattern. The number of QALYs for each patient will subsequently be calculated by interpolation between successive measurement and determining the area under the curve for the follow-up period of 12 months.

V7 01-02-2024 26 of 30

ETHICAL CONSIDERATIONS

